All subjects will complete the demographic form at baseline. The KCCQ (Appendix 2) and Vigor scale from the Profile of Mood States (POMS) will be completed in CTSU visits at baseline and 12 weeks (Appendix 3) along with the subject's height and weight. The patient will be escorted to a private room and asked to remove clothing above the waist. A disposable gown will be provided and the patient will lay supine on the bed while an echocardiogram is completed. Approximately 0.5 ml of blood will be collected via finger stick to measure lactate, ATP, and BNP. Next, the subject will complete a 6MWT (Appendix 4, Borg scale). Approximately 2 hours will be required for each subject's visit to the CTSU. Follow-up calls will occur at 3, 6, and 9 weeks during the trial.

Potential Problem and Alternative Solutions. Serum CoQ10 and D-ribose values in some of the treatment patients might be below threshold levels at 6 weeks, possibly due to subject non-adherence. If this occurs, the Project Director, who is not blinded to the list of placebo and treatment subjects, will call and ask if there are any problems with consuming the ubiquinol and/or D-ribose. The Project Director and Research Associate will conduct a phone follow-up interview at 3, 6, and 9 weeks during the trial using a structured interview. Questions asked will relate to any side effects and compliance history in taking their capsules or powder.

Various cardiovascular risk factors will be recorded such as tobacco usage, diabetes mellitus, hypercholesterolemia, hypertension, and family history of cardiovascular disease. Smoking status will be recorded as either smoker or non-smoker. Patients who use tobacco will be given contact information for a tobacco/smoking cessation program. Diabetes mellitus will be determined by a history of the disease or use of medication for diabetes. Hypercholesterolemia will be defined as a fasting total serum cholesterol level ≥ 4.9 mmol/l or use of medication. Hypertension will be defined as either systolic or diastolic blood pressure $\geq 140/90$ mmHg or use of hypertensive medications.

C.3. Aims and Hypotheses.

AIM #1: *To determine the effects of oral ubiquinol, D-ribose, or a combination of the two administered during 12 weeks on symptoms accompanying low bioenergetics in patients with HFpEF.*

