echocardiography on patients with HFpEF have demonstrated more sensitive measurements of changes of LV structure than regular echocardiography. Speckle tracking consistently showed early diastolic strain rate, reduced peak strain, and fibrosis as evidenced by increased myocardial reflectivity, which parallels the degree of diastolic dysfunction.⁵⁰⁻⁵² In this study, a speckle tracking echocardiography technician will perform the echocardiograms during each visit (baseline and 12 weeks). Drs. [name] (an expert in speckle tracking research), [name], and [name] (cardiologists) will determine EF and the ratio of mitral peak velocity of early filling (E) to early diastolic mitral annular velocity (e') (E/e' ratio) (SV, EDV, EF) from the echocardiogram. Using speckle tracking software, we will measure myocardial deformation, rotation, torsion, strain, strain rate, and tissue velocity. Changes in the early apical diastolic untwisting rate (rotR) and negativity of time from apical peak diastolic untwist (trotR) to mitral valve opening (MVO) are two major variables that reflect diastolic function. Decreases in rotR and trotR are indications of diastolic dysfunction.⁵³ Speckle tracking analysis with two-dimensional imaging will be performed as previously described by Leitman et al. at high frame rate parasternal short-axis images at the level of the mitral valve to generate rotation and rotation rate data.⁴⁷ Frame-by-frame rotation and rotation rate will be exported in Excel, and the temporal data will be normalized to the percentage duration of systole and diastole separately as previously described by Nakai et al.⁵⁴ We anticipate that ubiquinol and/or D-ribose will change rotR, trotR, strain, strain rate, and tissue velocity.

Potential Problem and Alternative Solutions. One issue that might arise relates to scheduling the echocardiographic technician when the subject is available to come to the CTSU. A solution is to utilize an additional on-call echocardiographic technician should scheduling issues occur.

Hypothesis #4. Ubiquinol (600 mg daily), D-ribose (15 g daily), or a combination of the two will increase the distance that patients with HFpEF can walk in 6 minutes.

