
A capillary finger stick blood sample (1.0 ml) will be obtained after subjects have completed the questionnaires and echocardiograms. Lactate concentration will be measured with a portable i-STAT handheld instrument using a CG4+ cartridge that requires 0.5 ml blood and takes 2 minutes to complete. Quality control tests will be performed on the i-STAT instrument each time prior to sampling. The lactate cartridge initiates a series of preset quality control diagnostics, from monitoring the quality of the sample to validating the reagent. The lactate cartridge contains sensitive biosensors on a silicon chip that is configured to perform that specific test. We will use 0.5 ml of venous blood for the ATP measurements and place it in 10 ml of distilled water. Using a probe called the AquaSnap Total system, ATP in solution will be measured. The specifically designed tip will collect 100 µl of solution, and then we will place the probe into the EnSURE™ instrument (ATP Test System). The EnSURE™ quality monitoring system detects real-time ATP down to 0.1 fmol within 15 seconds.

C.4. Preliminary Data. [name], our senior cardiologist, has more than 10 years of clinical experience in prescribing CoQ10, and for the past 4 years has prescribed the combination of ubiquinol (600 mg/day) and D-ribose (15 g/day) for patients with HFpEF. He has observed significant improvement in the health status of these patients using this combination of supplements. All subjects in our preliminary study reported that they complied with these doses by taking all daily required supplements in the morning with breakfast (compliance). Each subject tolerated these doses without any reported side effects (tolerance).

Table 1 summarizes the results of this preliminary study. Patients with HFpEF were given the KCCQ and the POMS Vigor subscale before and after 12 weeks of taking ubiquinol or ubiquinol plus D-ribose. We observed significant improvements (paired samples t-tests, $p < 0.05$) in the KCCQ clinical summary, functional status, self-efficacy, social interactions, quality of life, symptoms, and physical limitation scores as well as significant improvements in POMS Vigor scores. The increase in self-efficacy and social interactions was not a direct change but may have resulted from the improved level of vigor and reduced signs and symptoms of HF.

| Table 1 Variables | Ubiquinol Only (N = 5) | | Ubiquinol + D-ribose (N = 5) | |

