Hypothesis #4. A two-tailed independent samples t-test will be used to test the null hypothesis that the mean change in the 6MWT from baseline to the end of 12 weeks in patients taking ubiquinol is different from the mean change for placebo. Comparisons of D-ribose versus placebo, of ubiquinol + D-ribose versus placebo, and of ubiquinol versus ubiquinol + D-ribose will likewise be made. Our proposed sample sizes (62 per group) will allow detecting Cohen effect sizes on the 6MWT of at least 0.7 with at least 90% power at a nominal 0.05 level of significance with Bonferroni correction for four comparisons. Published data⁸⁶ suggest the possibility of a much larger effect size of ubiquinol on a 6-minute walk (3.9), giving us confidence in our design for at least the ubiquinol vs. placebo comparison.

Hypothesis #5. Our pilot data suggested that ubiquinol has a large effect size on BNP (-1.5 ; Table 2). Thus, two-tailed independent samples t-tests comparing changes in BNP from baseline to the end of 12 weeks will have a large power (99%) for investigating Hypothesis #5 using Bonferroni corrections. In general, our sample sizes will be able to detect effect sizes of at least 0.7 in absolute value with at least 90% power.

Hypothesis #6. The change in lactate/ATP ratio from baseline to 12 weeks will be computed for each patient. A one-tailed independent samples t-test will examine the null hypothesis of no differences in mean changes

between ubiquinol and placebo groups against the alternative that the mean change in patients on ubiquinol will be numerically smaller, which includes the possibility of a negative change. Similar tests will compare D-ribose versus placebo, the combination of ubiquinol + D-ribose versus placebo, and ubiquinol versus ubiquinol + D-ribose. Our sample sizes will give us a power of at least 90% to detect effect sizes of at least 0.7 in absolute value by using a 0.05 significance level and Bonferroni correction for the four comparisons.

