Statistical Analyses of Interaction. The study will give us an opportunity to examine whether there is an interactive effect with synergism on KCCQ scores when simultaneously administering ubiquinol and D-ribose. To investigate whether ubiquinol and D-ribose interact synergistically, a linear regression model of KCCQ score change from baseline to week 12 will be built. The model will include indicators for ubiquinol and D-ribose treatment as independent variables, as well as the product of these two indicators (the interaction term), gender, and race/ethnicity demographics. Analogous regressions will be conducted with KCCQ subscales, with the POMS Vigor score, as well as with indicators of left ventricular diastolic function. In addition, this study will give us an unparalleled opportunity to: (1) examine the mediating role of the lactate/ATP ratio in the effect of ubiquinol on left ventricular diastolic function in patients; and (2) examine whether there is an interactive effect with synergism on this function when simultaneously administering ubiquinol and D-ribose. A structural equation model will be built to explore our mechanistic⁸⁷ hypothesis that a reduction in lactate/ATP ratio mediates the association between ubiquinol treatment and reduction in E/e' ratio. We will control for potential confounders such as demographics, baseline lactate/ATP ratio, and baseline E/e' ratio. This modeling approach will take full advantage of the fact that subjects will provide measures of lactate/ATP and E/e' ratios at two time points (baseline and 12 weeks), which will allow disentangling the dynamic effects of time, a crucial variable in causality analyses. In a published article, [name] has described the use of structural equations in examining mechanistic pharmacological hypotheses of mediation.⁸⁸ Similar models will be built by using the other indicators of left ventricular diastolic function in place of E/e'. To investigate whether ubiquinol and D-ribose interact synergistically, a linear regression model of E/e' change from baseline to week 12 will be built that will also include as independent variables indicators for ubiquinol and D-ribose treatment, as well as the product of these two indicators (the interaction term), gender, and race/ethnicity. Analogous regressions will be conducted with other indicators of left ventricular diastolic function. If necessary, transformations will be performed to achieve the assumptions of regression models.

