1.1. Human Subjects Involvement, Characteristics, and Design. The involvement of human subjects in the work outlined in the Research Strategy includes two visits to the Clinical and Translational Scientific Unit (CTSU), obtaining echocardiograms and digital punctures (finger sticks), completing questionnaires, and receiving three follow-up phone calls by research staff. As suggested by the reviewers, we will oversample minority populations to increase the generalizability of data for minority groups (30% African American (AA), 30% Hispanic/Latino, 30% White, and 10% American Indian/Alaska Native, Asian, Native Hawaiian/Pacific Islander). All patients **included** in this study will: be 50 years old or older; have left ventricular ejection fraction (EF) $\geq 50\%$ documented by an echocardiogram within 12 months of enrollment; be diagnosed with HFpEF within a 12-month period; HFpEF, have symptoms of dyspnea and New York Heart Association (NYHA) Classification II or greater symptoms, have a diagnosis of HFpEF defined by one of the following: (1) previous hospitalization for HF with radiographic evidence (pulmonary venous hypertension, vascular congestion, interstitial edema, or pleural effusion) of pulmonary congestion, (2) invasive hemodynamics, (3) echocardiographic evidence of diastolic dysfunction, (4) elevated NT-pro (>400 pg/ml) or BNP (>200 pg/ml), or (5) no use of intermittent sublingual nitroglycerin within 12 months; be 50 years old or older; have left ventricular ejection fraction (EF) $\geq 50\%$ documented by an echocardiogram; are diagnosed with HFpEF within a 6-month period; have willingness to provide informed consent; have a telephone or reliable phone contact; and have their own means of transportation to the study site. Patients will be **excluded** based on any of the following criteria: (1) acute coronary syndrome in the past 12 weeks; (2) significant valvular heart disease; (3) severe cardiac fibrosis (galectin-3 level > 26 ng/ml); (4) constrictive pericardium; (5) pulmonary fibrosis; (6) congenital heart disease; (7) hypertrophic or infiltrative cardiomyopathy; (8) heart transplant; (9) left ventricular assist device; (10) HF associated hospital admission or emergency room visit within past 30 days; (11) recent percutaneous coronary intervention; (12) significant renal and/or hepatic dysfunction; (13) severe cognitive impairment; or (14) consumption of any CoQ10 (ubiquinol) or D-ribose supplements. Hepatic and renal dysfunction will be defined as an ICD-10 code with diagnosis of renal and/or hepatic failure in the patient's healthcare record. For retention we will schedule the sessions at a convenient time for each participant. Two nurse practitioners and a cardiologist on this application who work in the outpatient HF clinics will refer patients to the research team. Also, potential patients with HFpEF who are in the Frontiers participant registry will be contacted, screened, and enrolled in the study. In this randomized, double-blind, placebo-controlled trial, eligible subjects will be randomized to receive either ubiquinol (600 mg daily po), D-ribose (15 g daily po), a

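### Measuring lactate/ATP and E/e' at the same two visits does not identify the direction or causal reading of their link without assumptions the plan does not state

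*Combined protocol and SAP*

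**What the plan says.** Under Statistical Analyses of Interaction in C.5, the plan will build a structural equation model to explore whether "a reduction in lactate/ATP ratio mediates the association between ubiquinol treatment and reduction in E/e' ratio". It will adjust for demographics and for the baseline values of both ratios, and repeat the model for the other indicators of diastolic function. It presents the two measurement times as a strength, "which will allow disentangling the dynamic effects of time, a crucial variable in causality analyses".

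The schedule behind the model is set elsewhere:

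- **Mediator.** C.5, Hypothesis #6: "The change in lactate/ATP ratio from baseline to 12 weeks will be computed for each patient".
- **Outcome.** C.3 (Hypothesis #3) and C.5 place the echocardiogram, and so E/e', at baseline and 12 weeks.
- **Order within a visit.** C.3, Hypothesis #6: "A capillary finger stick blood sample (1.0 ml) will be obtained after subjects have completed the questionnaires and echocardiograms".
- **Contacts.** The human-subjects section (1.1) counts two clinic visits. Between them, C.2 provides only telephone contact: "Follow-up calls will occur at 3, 6, and 9 weeks during the trial".

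**The concern.** A mediation claim has three links: treatment to mediator, treatment to outcome, and mediator to outcome. Randomisation supports the first two. The third compares patients on a variable that was not randomised, so it needs either a time order or explicit assumptions. The plan appears to rely on time order, but mediator and outcome change over the same 12 weeks and are read at the same visit.

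The bioenergetic mechanism is central to the rationale in sections A and B. A significant indirect path could be read as evidence for it. The same path could arise if better filling lowered the lactate/ATP ratio, or if something unmeasured after baseline moved both. Because the model is repeated for the other diastolic indicators, the same ambiguity would recur with each.

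**Working it through.** The plan gives no power or effect-size figure for the mediation model, so there is no stated number to reproduce. The check has four steps.

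**1. Is there a post-treatment mediator value before the outcome?**

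| Time | Lactate/ATP | E/e' |
|---|---|---|
| Baseline visit | yes | yes |
| Weeks 3, 6, 9 | telephone call only | telephone call only |
| Week-12 visit | yes, after the echocardiogram | yes |

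Two passages suggest something at 6 weeks. Statistical Analysis of Effect of Treatment Duration (C.5) uses 6-week changes and extends the analysis to E/e', but its list omits lactate/ATP, and a two-visit schedule supplies no 6-week echocardiogram. C.2 mentions serum CoQ10 and D-ribose at 6 weeks, again not lactate/ATP. The post-walk lactate sample (Hypothesis #4) comes later in the same visit. So the answer is no.

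**2. Can model fit choose a direction?** Let X be treatment, M and Y the week-12 lactate/ATP and E/e', and Z both baselines plus demographics.

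- Forward: f(M | X, Z) × f(Y | X, M, Z)
- Reverse: f(Y | X, Z) × f(M | X, Y, Z)

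Both equal f(M, Y | X, Z). For linear Gaussian models with all of Z in every equation, the maximised likelihoods are therefore equal. A simulation agrees: with 2,000 runs per scenario, the largest log-likelihood difference was below 3 × 10⁻¹³. This does not depend on effect sizes.

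**3. How large is the spurious share if the direction is reversed?** Assume Y = aX + e_Y and M = gY + e_M, with unit residual variances and the baseline terms adjusted out. The planned model then estimates:

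- X to M: ga
- M to Y, given X: g/(1 + g²)
- indirect effect: ga × g/(1 + g²) = a·g²/(1 + g²), out of a total effect a

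The share labelled as mediated is g²/(1 + g²). The true share is zero.

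| g (assumed) | g²/(1 + g²) | Share |
|---|---|---|
| 0.2 | 0.04/1.04 | 4% |
| 0.3 | 0.09/1.09 | 8% |
| 0.5 | 0.25/1.25 | 20% |
| 0.7 | 0.49/1.49 | 33% |
| 1.0 | 1.00/2.00 | 50% |

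Nothing in the documents fixes g.

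**4. How often would it be significant?** The sizes used were 62 per treatment level (one arm against another) and 124 (2 × 62, if arms are pooled by ubiquinol). All effects are assumed.

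- *Reverse truth*, treatment effect −0.7, g = 0.5: both legs of the planned indirect path were significant in 40% of runs at 62 per level and 70% at 124.
- *Shared unmeasured cause, no M–Y path*: treatment effect −0.7 on each variable, shared cause weighted 0.7 and own error 0.71. The M-to-Y coefficient is 0.49/(0.49 + 0.71²) = 0.49/0.994 = 0.493, so the indirect effect is −0.7 × 0.493 = −0.345, about half of the total. Both legs were significant in 97% of runs at 62 per level and over 99% at 124.

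**The case against.** The best defence has four parts.

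- **The sentence claims less than it may seem to.** It says that two time points help to separate the effects of time. A reader might infer that the plan promises to establish which of lactate/ATP and E/e' drives the other, but the text does not say so. Two waves do separate baseline level from later change, and randomisation places treatment before both week-12 values. That stands. The remaining fault is that the sentence offers this timing as support for a causality analysis while the link in question has no time order.
- **Equal fit depends on the specification.** A reader might infer that direction can never be recovered from these data. That is too strong. The plan lists covariates but not which equation each enters. Suppose each week-12 value is regressed only on its own baseline, with no cross-lagged paths. With true direction E/e' to lactate/ATP, treatment effect −0.5, path 0.5, independent baselines and N = 248, the reverse model then fitted better in about 92%, 99% and 100% of 2,000 runs at assumed autoregressions of 0.3, 0.5 and 0.7. This stands, but it needs two restrictions the plan does not state: no cross-lags and no shared unmeasured cause.
- **The analysis is exploratory and adjusts for baselines.** Both are true. It tests none of Hypotheses 1–6. Baseline adjustment removes confounding by the measured baseline values, not by causes that act after baseline.
- **Mediator–outcome confounding is a general limit of mediation in randomised trials.** This is also true, and it is a reason to state the assumption and test sensitivity to it. The only sensitivity analysis described in C.5 concerns missing data.

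**Conclusion.** The point holds as a limited one. With both variables read at the same two visits and no lactate/ATP value between the start of treatment and the week-12 E/e', the lactate/ATP to E/e' link is not identified unless one assumes no shared unmeasured cause and, in addition, either a direction or the absence of cross-lagged paths. The plan states none of these.

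The identity of forward and reverse fit is exact when both equations carry the same covariates. The false-mediation shares, 4% to 50% for g from 0.2 to 1.0, rest on assumed paths and unit residual variances. A reader might take one value, such as 20%, as this trial's expected error, but the documents support no particular value.

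A reader might also infer that everything in this model is only associational. It is not: the treatment effects on lactate/ATP and on E/e' remain randomised comparisons. The consequence is confined to what the trial may say about mechanism.

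**What to change.** In C.5, Statistical Analyses of Interaction:

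1. Delete the claim that the two time points resolve time for causal purposes.
2. State the assumptions: no unmeasured mediator–outcome confounding, and either an assumed direction or no cross-lagged paths. Show which covariates enter which equation.
3. Report the indirect effect as an association consistent with mediation, and keep the two treatment effects as causal contrasts.
4. Add a sensitivity analysis over the residual correlation between mediator and outcome, for E/e' and for each of the other diastolic indicators. Report the correlation at which the indirect effect reaches zero.
5. Optionally, show the reverse model alongside. With the same covariates it fits equally well, so it displays the ambiguity and cannot choose a direction.

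The cost is a little more analysis and a weaker mechanistic statement from an exploratory model. No new data, visits or patients are needed, and Hypotheses 1–6 are unaffected.

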
come to the Clinical and Translational Science Unit (CTSU), a newly renovated facility with private examination rooms, pharmaceutical rooms, and storage area (for echocardiogram, i-stat instrument, etc.), and computer access to the Velos eResearch for patient data. The facility has plentiful free/close parking.

C.2. Study Design and Materials. Both HFpEF patients and stakeholders had a meaningful influence on the study design. We held focus groups, made individual phone calls, and had in-person meetings with patients with HFpEF. Our Stakeholder Advisory Panel (SAP) consists of diverse individuals including patients, caregivers, clinicians, and hospital administrators (Appendix 1) who have met three times. The patients and caregivers were particularly interested in whether ubiquinol, D-ribose, or both could enhance health status, decrease symptoms, and improve energy levels. We invited 30 HFpEF patients and their caregivers to provide input and feedback regarding the development of our research hypotheses and methods. We found their opinions extremely valuable in designing this patient-centered study.

Study Design, Including Screening, Enrollment, Visits, and Phone Follow-up (Figure 3).

Based on the power analyses (see C.5.), this randomized, double-blind, controlled trial will have a total sample size of (N) = 276. All participants will receive usual care for HFpEF. Efforts will be made to recruit 50% females, which is the actual proportion of HFpEF patients in Kansas City.

N1 = 69 subjects: Control, receive no ubiquinol and no D-ribose; placebo capsules & powder per day.
N2 = 69 subjects: Ubiquinol group, receive 600 mg of ubiquinol/day, D-ribose placebo powder per day.
N3 = 69 subjects: D-ribose group, receive 15 g of D-ribose/day, placebo capsules for ubiquinol per day.
N4 = 69 subjects: Ubiquinol + D-ribose group, receive 600 mg ubiquinol and 15 g D-ribose per day.

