Using the Vigor subscale from the POMS questionnaire,²⁹⁻³¹ patients will rate themselves on eight adjectives (lively, active, energetic, cheerful, alert, full of pep, carefree, and vigorous) on a five-point scale (0 = not at all, 1 = a little, 2 = moderately, 3 = quite a bit, and 4 = extremely). The Vigor scale has very high internal consistency (Cronbach's alpha = 0.90), and it takes only 1 minute to complete. In many studies it has been found to be effective for assessing vigor changes associated with exercise.³²⁻³⁴ The KCCQ and POMS Vigor scale will be administered to patients after they have been sitting quietly for 10 minutes at the beginning of each visit (baseline and 12 weeks). The total time for patients to complete both questionnaires will be 5 to 10 minutes. We anticipate that during the course of treatment the patients taking these supplements will report increasingly greater improvements in health status, daily functioning, and levels of energy.

Potential Problem and Alternative Solutions. Some older subjects may have difficulty reading the KCCQ or the POMS Vigor scale due to visual problems. We will have copies of both items in LARGE font available for those subjects. If that is not sufficient to solve the problem, we will read each item to the subject and complete the KCCQ and POMS Vigor scale for them if given verbal consent.

AIM #2: *To determine the effects of oral ubiquinol, D-ribose, or a combination of the two over 12 weeks on biological measures in patients with HFpEF.*

Hypothesis #3. Ubiquinol (600 mg daily), D-ribose (15 g daily), or a combination of the two will improve left ventricular diastolic function measured by advanced echocardiographic imaging in patients with HFpEF.

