Statistical Analysis of Effect of Treatment Duration. The effect of ubiquinol treatment duration on KCCQ Clinical Summary changes will be further investigated by fitting a random intercept linear model that will use the repeated measures provided by the subjects. Each subject will contribute to the model if any of the following two measures of the dependent variable are available: (1) a change in KCCQ score from baseline to the end of the 6th week, and (2) a change from baseline to the end of the 12th week. One dummy variable indicating whether the change corresponds to a treatment duration of 6 weeks (dummy=0) or 12 weeks (dummy=1) will be included as an independent variable as well as an indicator of ubiquinol treatment, gender, and race/ethnicity. This analysis will include subjects with complete or incomplete data. A positive and significant regression coefficient for the treatment duration dummy will signal that 6 weeks are not sufficient to obtain a change in KCCQ score equivalent to the change obtained after 12 weeks of treatment. Further, a significant regression coefficient for the ubiquinol treatment indicator will provide additional evidence of differences in KCCQ score changes between ubiquinol and placebo groups. To explore whether there is heterogeneity of ubiquinol effects across subjects, an additional random effects linear model will treat the regression coefficient of the ubiquinol indicator as a random coefficient. Analogous analyses will be made with the other continuous variables: POMS Vigor scale, E/e' ratio, PAP, and BNP and with D-ribose in place of ubiquinol. Random effects linear models use the information provided by participants with incomplete data such as participants discontinuing treatment. These models are robust to the presence of missing values under a missing-at-random assumption. To explore the sensitivity of the models to the presence of possible non-ignorable missing data, such as missing data caused by informative drop-out, a joint random intercept linear model will be fitted that will simultaneously model the KCCQ score and the missingness process.⁸⁹

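### The treatment-duration model needs week-6 outcome scores that the readable schedule does not collect, so its duration term cannot be estimated, and even with those scores its rule could not isolate ubiquinol

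*Combined protocol and SAP*

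**What the plan says.** **The model.** C.5, Statistical Analysis of Effect of Treatment Duration, fits a random-intercept linear model to "a change in KCCQ score from baseline to the end of the 6th week" and to the corresponding week-12 change. Its fixed effects are a dummy for duration (0 at 6 weeks, 1 at 12), a ubiquinol indicator, gender and race/ethnicity. A positive, significant dummy is to be read as showing that 6 weeks are too short. A significant ubiquinol coefficient is to count as further evidence of a difference from placebo. The section says that subjects with incomplete data are included, relies on missing at random, and adds a joint model of score and missingness as a sensitivity analysis. Vigor, E/e', PAP and BNP are to be treated in the same way, as is D-ribose in place of ubiquinol.

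**The schedule.** Under C.2, KCCQ and Vigor "will be completed in CTSU visits at baseline and 12 weeks". C.3 gives the same two times for the questionnaires (Hypothesis #2), the echocardiograms (Hypothesis #3) and BNP (Hypothesis #5).

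**Week 6.** C.2 states: "Follow-up calls will occur at 3, 6, and 9 weeks during the trial". On their content it says: "Questions asked will relate to any side effects and compliance history in taking their capsules or powder". The only other week-6 data mentioned are drug levels: "Serum CoQ10 and D-ribose values in some of the treatment patients might be below threshold levels at 6 weeks".

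**The concern.** The model takes its information about duration from a visit that the readable text does not provide for any of its outcomes. Three things depend on that visit: the duration coefficient, the separation of between-subject from within-subject variance, and the claim that subjects with incomplete data contribute.

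There is a second, conditional problem. The stated aim is the effect of ubiquinol duration, but the rule looks at a main effect of time that is common to both arms. If week-6 scores existed, improvement on placebo alone could trigger it.

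At stake are a planned analysis that cannot be run as written, a statement about missing data that the schedule does not support, and a rule that does not answer its own question.

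**Working it through.** **1. Outcomes in the model against the readable schedule**

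| Outcome | Where scheduled | Times given |
|---|---|---|
| KCCQ, Vigor | C.2; C.3 Hypothesis #2 | baseline, week 12 |
| E/e' | C.3 Hypothesis #3; C.5 Interaction (two time points for E/e' and lactate/ATP) | baseline, week 12 |
| BNP | C.3 Hypothesis #5 | baseline, week 12 |
| PAP | not scheduled explicitly; grouped with the echocardiographic data in C.4, Table 2 | none stated |

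The human-subjects sections 1.1, 1.3 and 2.1 count two clinic visits. They give the number of visits, not the weeks.

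**2. The plan's own figures.** The duration section states no number. The linked KCCQ calculation in C.5 uses a 10-point difference, SD 12.3, 62 per group and two-sided 0.05/4 = 0.0125.
- Standard error: 12.3 × √(2/62) = 2.209.
- Power: Φ(10/2.209 − 2.498) = Φ(2.03) = 0.979. The exact noncentral t gives 0.976. Both round to the stated 98%.
- Attrition: 62/0.90 = 68.9, so 69 per group and 276 in total. Completers are 4 × 62 = 248, leaving 28 without a week-12 score, or 7 per arm.

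No week-6 quantity enters any of this.

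**3. Fixed effects.** The columns are intercept, duration dummy, ubiquinol, gender and three indicators for the four race/ethnicity groups: 1 + 1 + 1 + 1 + 3 = 7. With week-12 rows only, the dummy is 1 throughout and equals the intercept column, so the rank is 6 of 7 and the dummy is not estimable. Without the dummy the rank is 6 of 6, so the ubiquinol coefficient is estimable. With rows at both weeks the rank is 7 of 7.

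**4. Variance components.** With one change score per subject, the likelihood depends only on the sum of the intercept and residual variances. For one simulated data set of 124 subjects, with the total fixed at 12.3² = 151.29, the splits 0 + 151.29, 75 + 76.29 and 150 + 1.29 all give a log-likelihood of −473.417.

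**5. Incomplete data.** A subject without a week-12 score has no change score and no row. The 28 expected dropouts are absent, and the model uses the same completers as the t-tests.

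**6. If week-6 scores existed.** Take the ubiquinol and placebo arms, 62 each with both scores. Let ΔP and ΔU be the mean week-6-to-12 changes on placebo and ubiquinol.
- Dummy: (ΔP + ΔU)/2, with standard error 12.3 × √(2(1 − ρ)/124).
- Duration-by-ubiquinol contrast: ΔU − ΔP, with standard error 12.3 × √(2(1 − ρ) × 2/62).

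The documents give no week-6 SD, within-subject correlation ρ or late change. SD 12.3 at week 6, the changes below and ρ of 0.3, 0.6 and 0.8 are therefore assumptions. Percentages come from 20,000 simulated trials per cell, with two-sided 5% tests.

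| ΔP / ΔU | Expected dummy | Dummy positive and significant, % (ρ = 0.3 / 0.6 / 0.8) | Expected contrast | Contrast significantly favours ubiquinol, % (same ρ) |
|---|---|---|---|---|
| 2 / 2 | 2.0 | 33.0 / 51.9 / 81.4 | 0 | 2.2 / 2.5 / 2.3 |
| 0 / 4 | 2.0 | 32.1 / 50.6 / 79.0 | +4 | 32.8 / 52.0 / 81.0 |
| 4 / 0 | 2.0 | 32.9 / 50.6 / 79.5 | −4 | 0.0 / 0.0 / 0.0 |

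Hand check at ρ = 0.6: the dummy's standard error is 12.3 × √(0.8/124) = 0.988, and Φ(2/0.988 − 1.96) = Φ(0.064) = 0.53. The rule fires about equally often whether the late gain is shared, all on ubiquinol or all on placebo. Only the contrast separates these cases.

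**The case against.** **Week-6 outcomes may be planned after all.** Figure 3 covers visits and phone follow-up and is not shown. The mention of week-6 serum levels implies some sampling at that time, which a count of two visits leaves unexplained. This stands as a limit. The text shows an inconsistency and does not show which side is the error. A reader might infer that the trial certainly collects no week-6 outcomes, but the documents do not support that. A week-6 assessment in the figure would still conflict with the sections cited and need reconciling.

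**Dropouts are not lost to every analysis.** This also stands. A reader might infer that subjects without a week-12 score contribute nothing anywhere. That is true of the change-score model only. The joint model could use their missingness and baseline score. It is not specified for two time points, but that does not make it unworkable.

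**The criticism of the rule is conditional.** Correct. Without week-6 data the dummy cannot be estimated and the rule never fires. The algebra is general, whereas the firing rates rest on the stated assumptions.

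**The analysis is supplementary.** Correct. The section presents it as further investigation. A reader might infer that the main comparisons or their power are compromised. They are not, since they use week-12 changes and already allow for 10% attrition.

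**The phone calls could supply week-6 KCCQ.** This is not clearly ruled out. The KCCQ takes 4 to 6 minutes (C.3, Hypothesis #1) and the calls last under 5 (Adequacy of Risk Protection). But the text limits the calls to side effects and compliance, and the Project Director, who shares the calling, is unblinded.

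**Conclusion.** The section is wrong as written when set against the readable schedule. The duration coefficient is not estimable (rank 6 of 7), and the random-intercept variance is not identified. The incomplete-data sentence fails in the change-score model for anyone without a week-12 score, about 28 of 276 at the planned attrition. These results follow from the schedule alone and need no numerical assumption beyond the 10%.

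If week-6 data existed, the rule still could not attribute a duration effect to ubiquinol, because the dummy averages over both arms. That too is algebraic.

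The ubiquinol coefficient survives as a covariate-adjusted comparison of week-12 changes among completers. The defect should be fixed before analysis, but its direct effect on the main results is small. The one open point is the content of Figure 3.

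**What to change.** Start by reconciling the duration section with the visit schedule and Figure 3, and state explicitly which outcomes, if any, are measured at week 6.

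**If none are:**
- Delete the duration analysis and its decision rule.
- Reword the incomplete-data statement to say that subjects without a week-12 score do not add to the arm contrast.
- Take the additional evidence on the arm difference from a baseline-adjusted week-12 model, such as ANCOVA. The missing visit does not by itself force this choice, but the model uses data already collected.
- State how the joint dropout model will be fitted to baseline and week-12 scores, or name another sensitivity analysis.

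**If some are:**
- Schedule them explicitly, with collection by blinded staff.
- Add the treatment-by-visit interaction and base the duration conclusion on it.

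The deletion route costs text changes only, with no new data, visits or subjects. Because this is a combined protocol and SAP, it is still a change to the protocol document. Scheduling new week-6 outcomes would be a protocol change that adds burden for participants and staff.
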